9.2 NUMBER OF SUBJECTS BY SITE AND JUSTIFICATION FOR SAMPLE SIZE

Approximately 60 eligible subjects will be enrolled and approximately 48 subjects are targeted to complete the study. Data from historical study CR 5758 and CR 5765 were used as the bench mark for sample size calculation because it tested the same population with the same study design and test article.

Using the POWER procedure in SAS 9.4, below is the summary of sample size required based on the different assumptions of the true difference. Each study hypothesis is tested with at least 90% of statistical power and 2-sided type I error of 0.05.

Several scenarios were listed in the table below to allow variations in the upcoming clinical trial:

| Difference (FU-Baseline) | Standard Deviation | # of subjects needed | Power |
|--------------------------|--------------------|----------------------|-------|
| 2 | 19 | 65 | 0.9 |
| 3 | 19 | 50 | 0.9 |
| 4 | 19 | 40 | 0.9 |

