2.6 DESCRIPTION OF POPULATION TO BE STUDIED, ENROLLMENT TARGETS, AND STUDY DURATION

The population to be studied will consist of Presbyopic Astigmats who have hyperopia and are adapted contact lens wearers currently wearing contact lenses. Approximately 60 subjects will be enrolled with a minimum of 48 subjects targeted to complete. The enrollment and study is estimated to last for approximately one month.

Distribution of the 48 Completed Hyperopes will be approximately 24 Against the Rule (ATR) and approximately 24 With the Rule (WTR)

| +0.75 to +1.50 ADD | | +1.75 to +2.50 ADD | |
|--------------------|-----|--------------------|-----|
| ATR | WTR | ATR | WTR |
| ≈12 | ≈12 | ≈12 | ≈12 |

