4.1 PRIMARY AND SECONDARY ENDPOINTS

The primary endpoint is overall quality of vision assessed using the Contact Lens User Evaluation questionnaire (CLUE™). CLUE is a validated Patient Reported Outcome (PRO) questionnaire developed to measure general and throughout the day comfort/vision, as well as symptoms of discomfort/poor vision, lens handling and packaging. Derived CLUE scores using Item Response Theory (IRT) follow a normal distribution with a population average score of 60 (SD 20), where higher scores indicate a more favorable/positive response. A 5 point increase in an average CLUE score translates into 10% shift in the distribution of scores for population of soft contact lens wearers.

The following one (1) primary hypothesis will be tested throughout this investigation. The primary hypothesis must be met to satisfy the objective of the study.

Primary Study Hypothesis

| | |
|---|--|
| 1 | After 12 to 16 days of wear, the CLUE vision score of the test lens will be non-inferior to subjects' habitual lens using a margin of -5 points. |
|---|--|

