9.1 STATISTICAL METHODS TO BE EMPLOYED

All data summaries and statistical analyses will be performed using the SAS software Version 9.4 (SAS Institute, Cary, NC). Throughout the analysis of data, the results for each subject/eye will be used when available for summarization and statistical analysis. Unscheduled visits will be summarized separately and will be excluded from the statistical analysis.

Summary tables (Descriptive statistics and/or frequency tables) will be provided for all baseline variables, efficacy variables and safety variables as appropriate. Continuous variables will be summarized with descriptive statistics (n, mean, standard deviation (SD), median, minimum and maximum). Frequency count and percentage of subjects or eyes within each category will be provided for categorical data.

Summaries will be presented by study lens type and will be performed separately by completion status (Completed or Non Completed). All analyses will be conducted on all subjects who completed the study (see section 9.7).

Primary Endpoint:

Overall quality of vision scores will be analyzed using a linear mixed model. The model will include the experimental design factors: time point (baseline/follow-up) as fixed effects. Other baseline characteristics known of importance such as age, gender, and/or add power will be included as fixed covariates when appropriate. Site will be included as random covariates when appropriate. The covariance between residual errors from the same subject across time points will be selected based on the finite-sample corrected Akaike's Information Criterion (Keselman et al. 1998). Covariance structures considered may include: Homogenous compound symmetry (CS) and Unstructured covariance structure (UN). The structure that returns the lowest Akaike Information Criteria Corrected (AICC) will be selected as the structure that best fit the data.

Comparisons between the time points will be carried out using 95% confidence intervals constructed of least-square means (LSM) differences (follow-up minus baseline) from the linear mixed model. The non-inferiority of the

test lens relative to the control will be concluded if the lower confidence limit of LSM difference is above the non-inferiority margin -5. The superiority will be established if the lower confidence limit is above 0.

In all models, the Kenward and Roger method (Kenward and Roger, 1997) will be used for the calculation of the denominator of degrees of freedom.

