9.3 LEVEL OF STATISTICAL SIGNIFICANCE

All planned analysis for this study will be conducted with an overall type I error rate of 5%.

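### Section 9.2 claims at least 90% power, but 48 completers fall short at true differences of 2 and 3, and the printed sample sizes fit two-sided 0.05 only with an unstated correlation

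*Combined protocol and SAP*

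**What the plan says.** Section 9.2 sets the size of the study: "Approximately 60 eligible subjects will be enrolled and approximately 48 subjects are targeted to complete the study". Section 2.6 words the target slightly differently: "Approximately 60 subjects will be enrolled with a minimum of 48 subjects targeted to complete".

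On power, Section 9.2 says: "Each study hypothesis is tested with at least 90% of statistical power and 2-sided type I error of 0.05". Its table gives three scenarios, each with SD 19 and power 0.9:

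| True difference (follow-up minus baseline) | Subjects needed |
|---|---|
| 2 | 65 |
| 3 | 50 |
| 4 | 40 |

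The test is defined in Section 9.1: "Comparisons between the time points will be carried out using 95% confidence intervals constructed of least-square means (LSM) differences". The criterion for success then reads: "test lens relative to the control will be concluded if the lower confidence limit of LSM difference is above the non-inferiority margin -5". The same section restricts all analyses to subjects who completed the study, so the sample size that matters for power is the number of completers. Section 9.3 adds: "All planned analysis for this study will be conducted with an overall type I error rate of 5", without saying whether this is one-sided or two-sided.

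Section 4.1 makes the study stand or fall on this test: "The primary hypothesis must be met to satisfy the objective of the study". It also says that derived CLUE scores "follow a normal distribution with a population average score of 60 (SD 20"), which is the SD of a single score and not of a change.

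**The concern.** Two things do not fit.

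First, 48 is below two of the three sample sizes that the table itself requires for 90% power. The power sentence carries no condition, and nothing says that 48 rests on the most favourable row.

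Second, the table does not say what SD 19 describes. It stands beside a column headed as a difference, and no correlation is given, so the natural reading is the SD of the within-subject change. On that reading the printed numbers do not follow from the stated two-sided 0.05.

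At stake is how a failed result would be read. A reader told that power is at least 90% would take a missed margin as evidence against the lens. If power is really 70% to 80% in a plausible scenario, a lens that is better than the habitual lens by 2 points would still miss the margin in roughly one study out of four or five.

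**Working it through.** **Inputs.** The margin is -5 and the rule is that the lower limit of a 95% confidence interval lies above it (Section 9.1), which is a one-sided 0.025 test. True differences 2, 3 and 4, SD 19 and power 0.90 come from the table in Section 9.2. There are 48 completers (Sections 2.6 and 9.2). The design is single-arm, with each subject's habitual lens at baseline compared with the test lens at follow-up, so the comparison is paired.

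**Formula.** For a paired t-test of the mean change against -5, with true difference d, SD of the change s and n subjects:

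- noncentrality = (d + 5) × √n / s, with n - 1 degrees of freedom
- power = P(T > t critical), where T is noncentral t and t critical is the 0.95 quantile (one-sided 0.05) or the 0.975 quantile (95% interval)

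**Step 1: reproduce the table with s = 19 (reading A).** The smallest n with power of at least 0.90 is:

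| True difference | Printed n | n at one-sided 0.05 | n under the 95% interval rule | Power at the printed n, 95% rule |
|---|---|---|---|---|
| 2 | 65 | 65 (0.902) | 80 (0.902) | 0.833 |
| 3 | 50 | 50 (0.902) | 62 (0.904) | 0.831 |
| 4 | 40 | 40 (0.903) | 49 (0.901) | 0.832 |

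The printed values match one-sided 0.05 in all three rows and two-sided 0.05 in none.

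**Step 2: try 19 as a per-visit SD (reading B).** With equal SDs at both visits and correlation r, s = 19 × √(2(1 - r)). Under the 95% interval rule the table comes out exactly as 65, 50 and 40 only for r of about 0.595 to 0.599, where s is 17.0 to 17.1. At r = 0.60 the first row is already 64. At r = 0.50, s is again 19 and the case is the same as reading A.

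**Step 3: power at 48 completers under the 95% interval rule.** For reading A the noncentralities are 7 × √48 / 19 = 2.55, 8 × √48 / 19 = 2.92 and 9 × √48 / 19 = 3.28, against t critical = 2.01 on 47 degrees of freedom.

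| True difference | Reading A (s = 19) | Reading B (r = 0.595 to 0.599) |
|---|---|---|
| 2 | 0.705 | 0.793 to 0.797 |
| 3 | 0.815 | 0.888 to 0.891 |
| 4 | 0.895 | 0.946 to 0.948 |

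The chance of missing the margin is one minus these values: about 29%, 18% and 10% on reading A, and about 20%, 11% and 5% on reading B. With 48 completers, 90% power needs a true gain of about 4.1 points on reading A and about 3.15 on reading B.

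**Step 4: sensitivity to the correlation.** The documents give no correlation, so it is an assumption. With a per-visit SD of 19 and the 95% interval rule:

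| r | n needed at 2 / 3 / 4 | Power at 48 |
|---|---|---|
| 0.4 | 95 / 74 / 59 | 0.626 / 0.742 / 0.835 |
| 0.5 | 80 / 62 / 49 | 0.705 / 0.815 / 0.895 |
| 0.7 | 49 / 38 / 31 | 0.898 / 0.958 / 0.986 |

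Forty-eight completers would reach 90% at a difference of 3 once r is about 0.61, and at a difference of 2 once r is about 0.70. At r = 0.70 the table would have to read 49, 38 and 31, so that value is ruled out by the plan's own figures.

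**Step 5: if all 60 enrolled subjects complete.** Reading A gives 0.802, 0.894 and 0.950. Reading B gives about 0.88, 0.95 and 0.98. A difference of 2 stays below 90% on both.

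**The case against.** The strongest reply is that the 90% figure is the condition used to compute each row, not a promise that 48 completers deliver it in every row. The table is introduced as a set of scenarios, and the reader can see that 48 lies between 40 and 50. On this view the gap is one of clarity. That reading is possible, but the sentence is unconditional and nothing names the row on which 48 rests, so the text still needs correcting.

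Second, the mismatch in sidedness depends on what 19 is. Section 4.1 gives 20 for a single CLUE score, so a per-visit 19 is plausible, and the historical studies behind it cannot be seen here. This stands: an error in alpha is shown only if 19 is the SD of the change. In favour of that reading, it fits all three rows with nothing left to choose, while the alternative needs a correlation that the plan does not mention.

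Third, the shortfall at a difference of 3 is about one point on reading B, which is trivial. If the printed values were rounded up to multiples of 5, a correlation of 0.6125 would give 62, 48 and 39, and 48 would reach 0.901 at a difference of 3. This also stands. The shortfall that holds firmly on both readings is the one at a difference of 2.

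Fourth, 48 is described as a minimum in Section 2.6, and 50 completers would meet the middle row on reading B. That is true, but on reading A even 60 completers give 0.894 at a difference of 3.

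Finally, this is a feasibility study. That limits the consequences, but the plan has chosen a formal pass or fail rule and attached a power claim to it.

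**Conclusion.** The concern holds. The claim of at least 90% power at two-sided 0.05 is not met by 48 completers at true differences of 2 and 3, on either reading of SD 19 that reproduces the table.

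- At a difference of 2, power is about 71% (reading A) or 79% to 80% (reading B), which is 10 to 19 points short.
- At a difference of 3, it is about 82% (A) or 89% (B). The gap is material on A and negligible on B.
- At a difference of 4, 48 is borderline on A (0.895) and adequate on B (about 0.95).

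The finding that the table was computed at one-sided 0.05 is conditional on 19 being the SD of the change. The figures rest on a simple paired t-test. The planned mixed model may adjust for covariates, and the plan gives no figures from which to estimate any gain from that. The decision rule is clear and the type I error is unaffected. The defect lies in the stated power and its basis.

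**What to change.** Keep the 95% interval rule and the target of 48 completers, and correct Section 9.2:

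1. State whether 19 is the SD of the follow-up minus baseline change or of a single score, and the sidedness used in the calculation.
2. If it is the SD of the change, replace 65, 50 and 40 with 80, 62 and 49. Replace the power sentence with wording such as: *With 48 completers and the 95% confidence interval rule of Section 9.1, power is about 71%, 82% and 90% (0.895) for true differences of 2, 3 and 4.*
3. If it is a per-visit SD, keep the table, state the correlation used, and give the power at 48 on that basis (about 79%, 89% and 95% if the correlation is 0.595 to 0.599).
4. Say which scenario supports 48. If 19 is the SD of the change, only a true gain of about 4 points does.

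The cost is a change of wording in one section and a less favourable power statement. No subjects, procedures or analyses are added.

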9.3 LEVEL OF STATISTICAL SIGNIFICANCE

All planned analysis for this study will be conducted with an overall type I error rate of 5%.

9.4 CRITERIA FOR STUDY TERMINATION

In addition to the stopping rules defined in section 9.1, the occurrence of one or more Serious Unanticipated Adverse Device Effect (USADE), or any SAE where the relationship to study agent cannot be ruled out, may result in stopping further dispensing of investigational product. In the event of a USADE or SAE, the Sponsor may unmask the treatment regimen for the subject(s) and may discuss this with the Investigator before any further subjects are enrolled.

The sponsor may determine when a study will be stopped. The principal investigator always has the discretion to initiate stopping the study based on subject safety or if information indicates the study's results may be compromised.

9.5 PROCEDURE FOR ACCOUNTING FOR MISSING, UNUSED, AND SPURIOUS DATA

Missing or spurious values will not be imputed. The count of missing values will be included in the summary tables and listings. If the percent of dropout is higher than 15% a sensitivity analysis will be conducted on all subjects who successfully tried at least one study lens.

9.6 PROCEDURE FOR REPORTING DEVIATIONS FROM STATISTICAL PLAN

The analysis will be conducted according to section 9.1. There are no known reasons for which it is planned to deviate from these analysis methods. If for any reason a change is made, the change will be documented in the study report along with a justification for the change.

9.7 EVALUABLE SUBJECTS

Subjects will be allocated to one of the three mutually exclusive groups:

1. Enrolled, Not Assigned: Subjects were considered to be Enrolled Not Eligible if they are (i) enrolled to the study (i.e. provided informed consent) but failed to satisfy the eligibility criteria (i.e. inclusion/exclusion criteria) or (ii) are not assigned to treatment for any reason.
2. Assigned, Not Completed: Subject are considered to have not completed the study from the study if they (i) were discontinued because of one the reasons described in section 5.1 or (ii) have successfully completed all required visits with a protocol deviation that the study responsible clinician documents as impacting the assessment of the hypotheses
3. Assigned, Completed: Subject are considered to have completed the study if (i) they are eligible, (ii) not discontinued (iii) have successfully completed all required visits without a protocol deviation that the study responsible clinician documents as impacting the assessment of the hypotheses.

10.1 ELECTRONIC CASE REPORT FORM/DATA COLLECTION

The data for this study will be captured on electronic case report forms (eCRFs) using an EDC system when possible. Designated study site personnel will enter study data into the electronic CRFs (eCRFs) using the EDC system. Data collected on equipment that is not possible to be captured in EDC will be formatted to the specification of the JJVC database manager and sent to JJVC for analysis. Data generated from post hoc measurements (e.g. Compositional characteristics of contact lens lipid uptake, Measured tear film protective capability, Measured contact lens surface dehydration rate) will be collected on specific Microsoft Office Excel format worksheets at the clinical site and at the completion of the analysis transferred to JJVC biostatistician for data analysis in such format.

External Data Source: Not Applicable or, if External Data is collected outside of EDC, please enter vendor contact information in this section of the protocol and type of external data collected.

Vendor Name: NA

Vendor Address: NA

Vendor Contact: NA

Phone: NA

Email: NA

Type of Data collected: NA

The CRFs will be reviewed for accuracy and completeness and signed by the investigator. Unless otherwise stated, the eCRFs will be considered the source document. The sponsor or sponsor's representatives will be authorized to gain access to the source documentation for the purposes of monitoring and auditing the study.

Edit checks, electronic queries, and audit trails are built into the system to ensure accurate and complete data collection. Data will be transmitted from the investigational site to a secure central database as forms are

completed or updated, ensuring information accuracy, security, and confidentiality. After the final database lock, the Investigator will be provided with Individual Patient Profiles (IPP) including the full audit trail on electronic media in a non-editable format for all of the study data. The IPP should be retained in the study files as a certified copy of the source data for the study.

The content and structure of the CRFs are compliant with ISO14155:2011 [3].

10.2 SOURCE DOCUMENTATION

At a minimum, source documentation should be available for the following to confirm data collected in the CRF: subject identification, eligibility, and study identification; study discussion, provision of and date of informed consent; visit dates; results of safety and efficacy parameters as required by the protocol; a record of all adverse events; follow-up of adverse events; concomitant medication; investigational product receipt / dispensing / return records; study investigational product administration information; date of study completion; reason for early discontinuation of investigational product or withdrawal from the study, if applicable.

The author of an entry in the source documents must be identifiable. Adverse event notes should be reviewed and initialed by the Investigator.

At a minimum, the type and level of detail of source data available for a study subject should be consistent with that commonly recorded at the site as a basis for standard medical care. Specific details required as source data for the study will be reviewed with the investigator before the study and will be described in the monitoring guidelines (or other equivalent documents).

10.3 ACCESS TO SOURCE DATA/DOCUMENT

The Investigator(s) / Institution(s) will permit trial-related monitoring, audits, IRB/IEC review and regulatory inspection(s) by providing direct access to source data / documents. Should the clinical site be contacted for an audit by an IRB/IEC or regulatory authority, JJVC should be contacted and notified in writing within 24 hours.

10.4 CONFIDENTIALITY OF INFORMATION

Information concerning the investigational product and patent application processes, scientific data or other pertinent information is confidential and remains the property of JJVC. The Investigator may use this information for the purposes of the study only. It is understood by the Investigator that JJVC will use information developed in this clinical study in connection with the development of the investigational product and therefore may disclose it as required to other clinical investigators and to regulatory agencies. In order to allow the use of the information derived from this clinical study, the Investigator understands that he/she has an obligation to provide complete test results and all data developed during this study to the Sponsor.

The Investigator may not submit for publication or presentation the results of this study without first receiving written authorization from JJVC. JJVC agrees that, before it publishes any results of the study, it shall provide the Investigator with at least 30 days for review of the pre-publication manuscript prior to the submission of the manuscript to the publisher.

11.1 DATA QUALITY ASSURANCE

Steps to be taken to ensure the accuracy and reliability of data include the selection of qualified investigators and appropriate study sites and review of protocol procedures with the principal investigator. The principal investigator, in turn, must ensure that all sub-investigators and study staff are familiar with the protocol and all study-specific procedures and have appropriate knowledge of the study article.

Guidelines for case report form completion will be provided and reviewed with study personnel before the start of the study. The sponsor, Johnson & Johnson Vision Care, Inc. will review case report forms for accuracy and completeness remotely during the course of the study, during on-site monitoring visits and after transmission to data management. Any data discrepancies will be resolved with the investigator or designee, as appropriate.

Quality Assurance representatives from Johnson & Johnson Vision Care, Inc. may visit study sites to review data produced during the study and to access compliance with applicable regulations pertaining to the conduct of clinical trials. The study sites will provide direct access to study-related source data/documents and reports for the purpose of monitoring and auditing by Johnson & Johnson Vision Care, Inc. and for inspection by local and regulatory authorities.

12.1 STUDY-SPECIFIC DESIGN CONSIDERATIONS

Potential subjects will be fully informed of the risks and requirements of the study and, during the study, subjects will be given any new information that may affect their decision to continue participation. They will be told that their consent to participate in the study is voluntary and may be withdrawn at any time with no reason given and without penalty or loss of benefits to which they would otherwise be entitled. Only subjects who are fully able to understand the risks, benefits, and potential adverse events of the study, and provide their consent voluntarily will be enrolled.

